PRECIS

Being overweight or obese can cause insulin resistance (IR), which is defined as reduced responsiveness to insulin by the cells of various tissues or organs. IR at midlife increases the risk of developing Alzheimer's disease (AD). We recently discovered novel biomarkers of brain IR (altered Tyr and Ser phosphorylated forms of insulin receptor substrate 1; IRS-1) in plasma exosomes enriched for neuronal origin. Moreover, IR is associated with AD biomarkers including deficits in resting state brain activity and cognitive performance. Calorie restriction is defined as consuming fewer calories than what is considered normal without a lack of nutrients. A certain type of calorie restriction, in which one consumes 500-600 calories a day for two consecutive days, followed by non-restricted eating for 5 days (5-2 CR), has been shown to lower peripheral insulin resistance effectively. Effects of CR and lowering peripheral IR on brain IR and cognition are unknown. The goal of this exploratory pilot study is to provide proof-of-concept that 5-2 CR at midlife can reverse brain IR, lower peripheral IR, improve cognitive performance, and increase brain activation at rest and during tasks. Specifically, we will study the effects of 8 weeks of 5-2 CR versus a control dietary intervention on brain and peripheral IR, memory and executive function, resting state default mode network activity, brain metabolism, and AD biomarkers. Forty overweight to obese women and men (between 55 and 70 years of age) will be randomized 1:1 into 5-2 CR and control groups. In the 5-2 CR group, participants will be offered "healthy living" dietary counseling at baseline, which they will be instructed to implement for five days/week. For each of the other two consecutive days/week, they will consume two shakes (Boost®, CWI Medical), providing a total of 480 Kcal/day. In the control group, participants will be offered "healthy living" dietary counseling at baseline, which they will be asked to implement for every day of the week. Participants will undergo screening including a history and physical examination, calculation of Body Mass Index (BMI, which must be ≥ 27) and a blood draw for insulin and glucose to determine whether they have insulin resistance. If participants meet eligibility criteria, they will continue with a baseline visit involving anthropometric measures, questionnaires, tests of cognitive function, brain MRI, blood draws for plasma and peripheral blood mononuclear cells, and lumbar puncture for cerebrospinal fluid biomarkers of AD. After 8 weeks, we will collect the same measures. To assess and reinforce compliance with their respective diet, participants will come into the clinic every 2 weeks to discuss compliance, measure their body weight and perform blood draws for measurement of ketones to objectively confirm energy restriction for the 5-2 CR group. We will also contact participants every week to further ensure compliance. To assess the effects of the diets on physical activity, participants will be asked to wear an accelerometer for 96 hours before and after they are on the diet.

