4.a.2. Compliance: We will assess and reinforce diet compliance with correspondence by telephone or electronic mail on week 1, 3, 5 and 7, as well as with Compliance Visits on weeks 2, 4, and 6. To assess compliance during Compliance Visits, we will be measuring plasma β -hydroxybutyrate. Values around 2-2.5 μ M/mL during CR days suggests compliance during 5-2 CR. β -hydroxybutyrate values of 0.5-1.0 μ M/mL suggest non-compliance with 5-2 CR, but would be expected for non restricted days and for the

control group.³⁹ In addition, we will be measuring body weight. Weight loss for 5-2 CR is expected to be about 2% per week based on our previous work.³⁹ Therefore, a progressive decrease seen after 2 weeks of 5-2 CR and persisting in the 5-2 CR group over 8 weeks suggest compliance to 5-2 CR,³⁹ while a smaller decrease in body weight is expected for the control group.

In addition, we will contact participants by telephone or electronic mail (using the Secure Email & File Transfer Service: <https://secureemail.nih.gov/bds/Login.do>) weekly to assess not only compliance with the diets, but also mood, level of energy, difficulty concentrating, headaches, feeling cold, constipation, negative emotions (sadness/depression, anxiety, irritability), hunger and preoccupation with food.^{39,40,94} For e-mail communications, we will provide participants with the web-address of the Secure Email & File Transfer Service with instructions on how to acquire login credentials.

4.b. Recruitment

Participants may be recruited through direct advertisement. Brochures and flyers will be used. Recruitment letters may be mailed to health care providers and to those participants who have requested information. We may place ads and/or public service announcements (PSA) on websites, in radio broadcasts, television, as well as newspapers, newsletters, and magazines. Direct mailing through established marketing and advertising organizations might also be used. Pre-screening over the telephone will utilize the eligibility checklist. Participants that we believe are likely to be eligible will come to the NIA-Clinical Research Unit to undergo screening.

We anticipate an accrual rate of 2-6 participants per month.

4.c. Screening

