Plasma ketones are strongly affected by alternate day CR acutely but not chronically;³⁹ our main objective for measuring them is to assess compliance with 5-2 CR.

We do not anticipate a change in physical activity in 5-2 CR versus “healthy living” control groups, because no change has been noted in our previous studies. Nonetheless, this is a common analysis requested by reviewers, to make sure that exercise effects did not contaminate diet effects.

The data from the gene array and DNA methylation array will be analyzed using residuals after adjustment for white blood cell differential count in linear regression models. We will take two approaches to analyze the data. First we will focus on candidate genes approach where we select specific expression probe or CpG sites; DNA for these studies will be collected during Baseline, Compliance and Outcome Visits. Second, we will run genome-wide association analysis for differences in cross sectional and longitudinal changes in gene expression or DNA methylation between the control and 5-2 CR group at each gene array probe or CpG site. DNA for genome-wide association analyses will only be collected during Baseline and Outcome Visits. For the cross sectional analyses, we will use a paired t-test at each visit, and mixed models for longitudinal analysis. In addition, we will look at overall patterns of gene expression and methylation using principle components, DIANE and hierarchical clustering tools to determine whether there are specific gene expression and methylation signature in association with 5-2 CR. As secondary analyses, we will also determine whether gene expression and DNA methylation patterns can predict the changes in metabolic, cognitive and neurochemical variables collected in this study. Within the 5-2 CR group, we will test the association between baseline levels of gene expression or DNA methylations at each probe/CpG site with longitudinal changes in the main outcome variables using mixed models.

10. b. Power analysis

The accrual number request is 100 participants. Our target sample size for completing the study is $N = 40$. There will be 20 participants in each group. We anticipate up to 60 participants will not meet inclusion criteria during the screening visit or may withdraw from the study. Enrollment will continue and withdrawals will be replaced until we have acquired complete data from 40 participants.

For power calculations, we used G*Power (<http://www.gpower.hhu.de/en.html>).

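### The stated model for plasma ketones omits the Week 2, 4 and 6 beta-hydroxybutyrate samples drawn to confirm restriction, and the two compliance bands in 4.a.2 leave 1.0-2.0 unread

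*Combined protocol and SAP*

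**What the plan says.** The plan gives the ketone measurement a definite job. The Precis describes "measurement of ketones to objectively confirm energy restriction for the 5-2 CR group". Section 10.a says of plasma ketones that "our main objective for measuring them is to assess compliance with 5-2 CR".

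Section 4.a.2 gives the reading guide. "Values around 2-2.5", in a unit printed as micro-M/mL, "during CR days suggests compliance during 5-2 CR". Values of 0.5-1.0 "suggest non-compliance with 5-2 CR, but would be expected for non restricted days and for the" control group. The same paragraph adds a second measure: "In addition, we will be measuring body weight".

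The other relevant places are:

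- **Table 2** schedules beta-hydroxybutyrate at Baseline, at Weeks 2, 4 and 6, and at Outcome.
- **4.d.4** puts the Compliance Visits on the second restricted day for the 5-2 CR arm and on any day for controls, after an 8-hour fast.
- **4.d.2** has Baseline blood drawn after a 12-hour fast.
- **4.d.1** times the Outcome Visit for the 5-2 CR arm on the second restricted day; **4.d.5** times it on the first.
- **Section 2 (aim 10) and 9.b** list plasma ketones as a secondary outcome.
- **10.a** prescribes, for the primary and each secondary scalar outcome, a mixed model with Group, Time and their interaction, where Time has two levels, Baseline and Outcome.

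**The concern.** A measure meant to confirm restriction objectively needs either a complete reading rule or a stated analysis. The reading guide is incomplete: two people scoring a value of 1.4 could disagree while both follow 4.a.2. The stated analysis leaves out the visits designed for the purpose. It relies instead on one post-baseline sample whose place in the weekly cycle is contradictory.

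The timing matters because 10.a itself says that intermittent restriction affects ketones acutely and not chronically. A sample from the first restricted day and one from the second may therefore not measure the same thing.

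What is at stake is interpretation. If the primary exosomal result is null, the first question will be whether the 5-2 CR arm restricted. If it is positive, readers will want it tied to demonstrated restriction. Both answers should come from an analysis fixed in advance.

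**Working it through.** **1. Width of the gap.** The non-compliant band ends at 1.0 and the compliant band starts at about 2, so 2.0 - 1.0 = 1.0 unit has no reading. Values below 0.5 or above 2.5 are also unlabelled, but their direction is clear from the text.

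**2. Share of restricted samples in the gap.** The plan gives no figure to reproduce and no SD, so the means and spreads below are assumptions. For a normal distribution with mean m and SD s, the share is Phi((2-m)/s) - Phi((1-m)/s).

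| Assumed mean | SD 0.125 | SD 0.25 | SD 0.5 | SD 1.0 |
|---|---|---|---|---|
| 2.0 (lower edge of band) | 50.0% | 50.0% | 47.7% | 34.1% |
| 2.25 (midpoint) | 2.3% | 15.9% | 30.2% | 29.6% |
| 2.5 (upper edge) | 0.0% | 2.3% | 15.7% | 24.2% |

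Worked cell: m = 2.25, s = 0.5 gives Phi(-0.5) - Phi(-2.5) = 0.3085 - 0.0062 = 30.2%. With 20 participants x 3 Compliance Visits = 60 planned samples in the 5-2 CR arm, that is about 18. At SD 0.125 it is about 1 of 60. With mean 2.25 the normal share peaks at 32.4%, at an SD of about 0.68. A lognormal with median 2.25 gives 12% at CV 10%, 28% at CV 20%, and 33-36% for CVs of 30-70%. The range is therefore about 0% to 50%, and the documents do not say where the trial lies in it.

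**3. What each sample is used for.**

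| Visit | Fast | Restricted day (5-2 CR arm) | In the 10.a model? |
|---|---|---|---|
| Baseline | 12 h | before the diet | yes |
| Weeks 2, 4, 6 | 8 h | second | no |
| Outcome | 12 h | second (4.d.1) or first (4.d.5) | yes |

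The three visits with one consistent day are the ones left out. The one post-baseline visit that is included has two stated days.

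**4. Could a group contrast show restriction?** Take the band midpoints as arm means: 2.25 - 0.75 = 1.5. Assume SD 1.0, 20 per arm and two-sided alpha 0.05, and use the normal approximation: power = Phi(difference / (SD x sqrt(2/20)) - 1.96).

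- Level at one visit: 1.5 / (1.0 x 0.316) = 4.74; Phi(4.74 - 1.96) = 99.7%.
- Change from Baseline has SD 1.0 x sqrt(2(1 - r)). If r = 0.4 (the correlation that 10.b assumes for the primary outcome), SD = 1.095; 1.5 / (1.095 x 0.316) = 4.33; Phi(2.37) = 99.1%.
- If r = 0, SD = 1.414; 1.5 / (1.414 x 0.316) = 3.35; Phi(1.39) = about 92%.

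Even with an SD that would put nearly 30% of restricted samples in the gap, a continuous contrast at a single visit is well powered.

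**5. Why the contrast must be between arms.** Baseline follows 12 hours of fasting and the Compliance Visits follow 8. Change within the 5-2 CR arm mixes diet with fast length. Both arms share the 12-to-8-hour shift, so the difference in change removes it, provided that fast length acts similarly in the two arms.

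**The case against.** The strongest reply is that 4.a.2 is not a classification rule. Its wording is soft, it describes expected levels taken from a cited study, and no analysis set, per-protocol population or withdrawal criterion depends on a band. Section 8.a explains persistent non-compliance as a matter of keeping follow-up visits. All of that stands, and it means that the gap alone would be a minor wording matter.

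A reader might also infer several stronger points that the documents do not support:

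- **That about a third of restricted samples would be unclassifiable.** This needs an assumed mean and spread, and other equally permissible choices give anything from near zero to one half.
- **That restriction cannot be confirmed, or that ketones are the only objective evidence.** Body weight is objective, is measured at every Compliance Visit, and has an expected difference between arms. Its benchmark does need reconciling: 4.a.2 expects about 2% per week, while the Introduction reports about 8% over 8 weeks from the same cited study, or 8/8 = 1% per week. That does not stop weight from being compared between arms.
- **That the plan ignores Baseline ketones.** Plasma ketones are a secondary outcome, so the 10.a model already compares Baseline with Outcome by group.
- **That the printed unit shifts the cut-offs a thousandfold.** It reads as a slip for umol/mL, is the same for both bands, and does not affect the gap.

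What the reply does not answer is that the Week 2, 4 and 6 samples have no stated beta-hydroxybutyrate model and that the timing of the Outcome sample conflicts.

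**Conclusion.** The point holds as an incomplete specification that is cheap to improve. Nothing here invalidates the primary analysis, which does not use ketones. The reading guide has a 1.0-unit gap, and the share of samples in it is unknown. The firmer finding rests on the text alone: three consistently timed compliance samples per participant, 60 per arm if all are obtained, are outside the stated beta-hydroxybutyrate model, while the Outcome sample inside it is assigned to two different days. The power figures assume arm means at the band midpoints and an SD of 1.0. They show only that a group contrast is feasible. Such a contrast speaks to restriction around the scheduled visits; given the acute nature of the marker, it is not a full record of adherence over 8 weeks.

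**What to change.** - **10.a:** add a mixed model for continuous beta-hydroxybutyrate with Group, Time (Baseline, Weeks 2, 4 and 6) and their interaction. Name the between-arm contrast in change from Baseline, with its confidence interval, as the group-level evidence of restriction. State that change within the 5-2 CR arm alone will not be used for this, because of the 12-hour and 8-hour fasts.
- **4.a.2:** say that the two bands are descriptive and define no analysis, and print the unit as umol/mL (mmol/L).
- **4.d.1 and 4.d.5:** reconcile the day of the Outcome Visit, so that the Baseline-to-Outcome ketone comparison has one meaning.

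The cost is a few sentences and one more model on samples that Table 2 already schedules in both arms. No new visits, draws or assays are needed.

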disorders, such as untreated subclinical hypothyroidism with TSH < 10 mU/l or successfully treated hypothyroidism may be allowed);

- 5. History of eating disorders, significant GI disorders or malabsorption disorders;
- 6. History of type 2 diabetes; and/or use of anti-diabetes medications or insulin; and/or type 2 diabetes diagnosed during the screening visit based on fasting glucose > 125 mg/dL;
- 7. History of hypoglycemia; and/or a fasting glucose < 70 mg/dL during the screening visit.
- 8. Current use of systemic corticosteroids;
- 9. Positive screening tests for HIV, HCV or HBV;
- 10. Hematocrit less than 35% or hemoglobin less than 11 mg/dL;
- 11. ALT or AST > 1.5 times the upper normal limit;
- 12. Contraindications for MRI (pacemakers, ferrous metal implants or shrapnel in or around the head, etc.).
- 13. Contraindications to LP, such as Coumadin, coagulopathy (international normalized ratio, or INR > 1.5; prothrombin time (PT), partial prothrombin time (PTT) > 1.5 x upper normal limit). Aspirin 81 mg qd is allowed. Aspirin up to 325 mg qd is allowed, if withheld for 7 days prior to the LP.
- 14. Pregnancy or nursing.
- 15. Refusal to consent to genetic testing for APOE.

4. Study Design and Methods

4.a. Study overview

This study is a randomized clinical trial, where participants will be assigned into two groups. In the 5-2 CR group, participants will be offered “healthy living” dietary counseling at baseline, consisting exclusively of published literature from the CDC and USDA, which they will be instructed to implement for five days/week. In addition, they will be instructed to consume only two shakes (Boost®, CWI Medical) providing a total of 480 Kcal/day for two consecutive days/week. In the control group, participants will be offered “healthy living” dietary counseling at baseline, which they will be instructed to implement for every day of the week.

Should a participant not be able to keep their scheduled study visits due to an unforeseen circumstance, and they are on 5-2 CR, she or he may be asked to implement CR on another day, or to extend the 5-2 CR diet for an additional week. Voluntary dropouts will be replaced until we have acquired complete data from 40 participants.

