4.a.1. Experimental conditions: Both groups will receive “healthy living” brochures published by the CDC and USDA at baseline. In the 5-2 CR group, participants will be encouraged to implement “healthy living” diet for five days/week, and not to intentionally overeat. For 2 consecutive days per week, participants in the 5-2 CR group will consume 480 kilocalories in the form of two meal replacement shakes (Boost®, CWI

Medical). These shakes will be supplied at the end of the Baseline Visit, as well as during the Compliance Visits every 2 weeks. This dietary regimen achieves about 20% net restriction compared to their weekly caloric intake, assuming a baseline 2000 Kcal/day intake. Participants in the 5-2 CR group will have the opportunity to taste the meal replacement shake (Boost®, CWI Medical) at the end of the Baseline Visit and choose a flavor they prefer. In the control group, participants will be encouraged to follow the “healthy living” diet every day.

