The study is comprised of: an initial telephone pre-screening to describe the study and inclusion/exclusion criteria to potential participants; a "Screening Visit"; randomization into one of two groups; a "Baseline Visit"; the "Outcome Visit" after 8 weeks. During the 8-week period for the 5-2 CR or control groups, participants will return every two weeks for "Compliance Visits", to assess and reinforce dietary compliance in keeping with previous protocols.^{39,40,94} The Outcome Visit will take place at the conclusion of the 8-week phase. Specifically for the 5-2 CR group, the Outcome Visit will be timed during the second of the two CR days. In total, there will be 6 outpatient visits to the NIA Clinical Unit: Screening Visit, Baseline Visit, Week 2 Compliance Visit, Week 4 Compliance Visit, Week 6 Compliance Visit, and the Week 8 Outcome Visit. There will be an additional follow-up phone call or electronic mail within 3 days of completing the Week 8 Visit to assess any problems related to their final visit. Accelerometry will be implemented on two occasions for 96 hours each time: once between the screening and baseline visits and again after the Week 8 Outcome Visit. Throughout the study, additional safety visits may take place for any clinically significant. Participants will be involved in the study for approximately 8 – 11 weeks (allowing for an up to 3 week gap between Screening and Baseline Visits). Study participation will end with completion of accelerometry after the Week 8 Outcome Visit.

It is anticipated that participants in this study will occasionally miss or fail to complete an assessment or procedure, such as a completion of a rating scale or a blood draw. Omissions such as these will be considered expected events and not protocol deviations provided they are infrequent and do not include data needed to assess safety or the primary study outcome. Cumulative proportions of these missed events in the study population will be presented to the IRB annually. In addition, the rate of omissions will be monitored by the Investigators. If an individual misses more than 15% of the required assessments/procedures or if more than 15% of the participants miss completion of the same assessment or procedure, it will be considered a deviation and a deviation report

will be sent to the IRB within two weeks.

Table 1: Procedures

Procedures	Visit 1	Visit 2		Visit 3, 4, 5	Visit 6	
		Week 0		Weeks 2, 4, 6	Week 8	

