measurements (weight, waist circumference, sagittal diameter) will be done. Participants will provide feedback regarding physical and psychological symptoms by completing a Symptoms Review Questionnaire and the RAND SF-36. Samples for β -hydroxybutyrate levels will be sent to Harbor Hospital Lab. In addition, a plasma sample will be sent to the NIA Core Lab for future studies. These visits will take about 1 hour.

In addition, blood will be collected for isolation of total RNA and genomic DNA for target pathways gene expression and methylation analyses, and PBMCs counts. 62 ml of blood will be collected during each one of these visits.

4.d.5. Outcome visit

The Outcome Visit will occur at the end of the 8-week period in the 5-2 CR or control group. This visit will take place during the first of the two consecutive constriction days for 5-2 CR participants or at a convenient time during the week for control participants. This visit will occur after a 12-hour fast, to ensure comparability of the mixed meal test with the Baseline Visit. The visit procedures will be similar to the Baseline Visit, including a lumbar puncture (LP) and a medical history and physical exam.

Participants will arrive on the NIA-Clinical Research Unit after a 12-hour fast. The following procedures will be done: vital signs, anthropometric measurements (weight, waist circumference, sagittal diameter), and a blood draw for clinical labs (CBC, PT, PTT, INR, CMP, lipid panel, uric acid, HgbA1c, insulin, β -hydroxybutyrate), urine pregnancy test (only in women who are able to become pregnant), and research labs including DNA collection (for gene expression studies). A 4-hour mixed meal tolerance test will be done. They will also have cognitive testing and will be asked to complete the Symptoms Review Questionnaire, PANAS, and RAND SF-36. A lumbar puncture (LP) will take place and up to a total of 15 mL of CSF will be collected. Participants will also have a brain MRI. About 174 mL of blood will be taken during each visit (including clinical and research labs). To facilitate scheduling or satisfy a given participant's request, we may split the various procedures of the Outcome Visit over two days within a week from each other.

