4-hour mixed meal tolerance test: After fasting for at least 12 hours, participants will be asked to drink 5 mL/Kg of the dietary supplement shake Ensure Plus®. Ensure Plus® is a mixed liquid meal; one bottle (480 mL) contains 95 g carbohydrate as dextrose, 26 g protein, and 25 g fat, providing 710 kilocalories. In addition, to inducing a change in glucose and insulin, the mixed meal tolerance test is ideal for testing changes in GLP-1, GIP, ghrelin, glucagon, pancreatic polypeptide, C-peptide, and other hormones. A blood draw will take place before subjects consuming the liquid meal. Plasma, serum and whole blood biomarkers will be measured from this blood draw. for biomarkers, hormones, and cytokines (approximately 35 mL). Then subjects will ingest the liquid meal, followed by blood draws every 20 minutes (5 mL per sample). Typically, participants will have an intravenous (IV) line placed in an arm vein for blood draws.

Lumbar puncture (LP): Participants will have LPs performed during the Baseline Visit and Outcome Visit at 8 weeks, to provide CSF for measurement of biomarkers. Up to a total of 15 mL of CSF will be collected on each of those two visits. CBC, PT, and PTT results should be available prior to each LP taking place. Participants will be encouraged to be well hydrated on the day of the LP.

In individuals in whom a landmark-guided LP at the bedside is deemed technically difficult by the medical staff (such as in the presence of degenerative lumbar spine disease, prior lumbar spine surgery, kyphosis/scoliosis or other conditions) or fails, a licensed Interventional Radiologist may perform the procedure under ultrasound or X-ray guidance (fluoroscopy-guided LP).

Cognitive testing: Logical Memory and CVLT will be administered using standard procedures. The MMSE will be administered only during the Screening Visit. In addition, we will administer EXAMINER, a software program (<http://examiner.ucsf.edu/index.htm>) implementing a battery of neuropsychological tests that reliably and validly assesses domains of executive function. This software was kindly given via a technology transfer request from [name] at the University of California – San Francisco. We will assess working memory, inhibition, set shifting, fluency, planning, insight, and social cognition and behavior. Neuropsychological testing will take approximately 1 hour to complete.

Brain MRI: In total, structural MRI, fMRI and MRS will last about 2 hours.

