This is a pilot study that is exploratory in nature and one of its goals is to collect preliminary data for multiple outcomes that may be used in future studies on the brain effects of CR.

For the primary and each secondary scalar measure, a separate repeated measures mixed models analysis will be conducted to examine the effects of the between-subjects factor “Group” (5-2 CR group vs. “Healthy living” control group), the within-subjects factor “Time” (Baseline vs. Outcome) and their Interaction. An Auto-Regressive (AR)1 covariance matrix and Restricted Maximum Likelihood Estimation (REML) will be used. We will assess fit to the model using the AIC and BIC criteria (lower values indicate better fit). These parameters were chosen because they are recommended for repeated measures analyses, including fMRI task analyses.¹⁰⁰ Regarding within-subjects effects, we will assess post-hoc differences between the 8-week outcome visit and baseline for the 5-2 CR and control groups and for each group separately (i.e. post-hoc tests for the Group * Time interaction). This analytic approach is common in the CR literature.¹⁰¹ Mixed model post-hoc tests will employ the Least Significant Difference (LSD) statistic. We will use one-tailed t-tests.

Criteria for significance will be set at alpha of 0.05 for all non-MRI analyses, and 0.005 uncorrected at the voxel level for fMRI analyses. Given that this pilot study is exploratory, we will not conduct correction of multiple comparisons for the various secondary outcomes.

Analysis of fMRI data will use a mixed model design to assess the effect of Group on

brain activation associated with viewing appetitive vs. non-appetitive food, the Stroop effect in the Stroop task, and DMN intrinsic functional connectivity. Analyses will be conducted at the whole brain level and within ROIs (vmPFC, OFC and insula for the fMRI food task, lateral and dmPFC for the Stroop task, and in DMN for resting state. The fMRI analyses will be corrected for type 1 error as the cluster level using Monte Carlo simulations.

For brain MRS measures, a repeated measures analysis will be separately used for each of the brain regions of interest: the hippocampus and the prefrontal cortex.

APOE genotype is a common covariate used when assessing populations with AD or at risk for AD. We intend to perform exploratory analyses including APOE, which may reduce error variance and improve our statistical models.

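### Sections 4.d.1 and 4.d.5 place the week-8 Outcome Visit of the 5-2 CR arm on different restriction days, and the split-visit clause names no diet day

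*Combined protocol and SAP*

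**What the plan says.** Section 4.d.1 (chronological ordering of procedures) states: "Specifically for the 5-2 CR group, the Outcome Visit will be timed during the second of the two CR days". Section 4.d.5 (Outcome visit) states: "This visit will take place during the first of the two consecutive constriction days for 5-2 CR participants". Both sentences concern the same visit and the same arm. Controls attend at a convenient time.

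Section 4.d.5 requires a 12-hour fast, to keep the mixed meal test comparable with Baseline. It adds that "we may split the various procedures of the Outcome Visit over two days within a week from each other". It does not allocate procedures to the two days or say that either must be a restriction day. Tables 1 and 2 show week 8 as a Day 1 and an optional Day 2, with no diet day.

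Section 4.a covers a 5-2 CR participant who cannot keep a scheduled visit: "she or he may be asked to implement CR on another day, or to extend the 5-2 CR diet for an additional week". For the draw taken before the liquid meal, section 4.d.6 says "Plasma, serum and whole blood biomarkers will be measured from this blood draw". The model in section 10.a, used for the primary and each scalar secondary measure, has Group, Time ("Baseline vs. Outcome) and their Interaction") and no other time point.

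**The concern.** The Outcome Visit yields the week-8 exosome sample for the primary outcome, and also the mixed meal test, CSF, MRI and cognitive testing. With two contradictory timing rules, the week-8 value in the 5-2 CR arm may or may not carry an acute effect of a just-completed restricted day. If staff follow different sections on different occasions, the arm becomes a mixture of the two states. The control arm has no counterpart to this, so any such effect would enter the Group by Time contrast directly.

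The problem could not be reliably undone afterwards. Restriction days may be moved under section 4.a, so the calendar does not reliably give the diet day, and no section requires the diet day to be recorded.

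**Working it through.** **1. The two rules side by side.** Section 4.d.1: second restriction day. Section 4.d.5: first restriction day. Section 4.d.4 fixes the week 2, 4 and 6 Compliance Visits on the second day but does not govern the Outcome Visit. The tables are silent. No text resolves the conflict.

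**2. Time since the last completed restricted day.** The Precis describes two consecutive restricted days "followed by non-restricted eating for 5 days (5-2 CR"). Write the weekly cycle as C1, C2, N1, N2, N3, N4, N5, and assume no restriction day is moved.

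- Visit on C2 (4.d.1): the preceding day is C1, so the last completed restricted day is 1 day earlier.
- Visit on C1 (4.d.5): counting back gives N5, N4, N3, N2, N1, then C2, so it is 6 days earlier, with 5 non-restricted days between.

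**3. Intake on the preceding day.** A restricted day is 480 kcal (section 4.a). Section 4.a.1 computes the net restriction "assuming a baseline 2000 Kcal/day intake". Intake on a non-restricted day during the diet is not given, so a range of 1600 to 2400 kcal is assumed.

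| Non-restricted day (kcal) | Gap (kcal) | Gap as share |
|---|---|---|
| 1600 (assumed) | 1600 − 480 = 1120 | 1120/1600 = 70% |
| 2000 (plan's figure) | 2000 − 480 = 1520 | 1520/2000 = 76% |
| 2400 (assumed) | 2400 − 480 = 1920 | 1920/2400 = 80% |

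This applies to the pre-meal blood sample, which is fasting. The order of lumbar puncture and MRI relative to the test meal is not stated, so no such claim is made for them.

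**4. Does diet day matter for any measured outcome?** For ketones, yes, on the plan's own figures. Section 4.a.2 expects β-hydroxybutyrate of about 2–2.5 on restricted days and 0.5–1.0 on non-restricted days, a ratio between 2/1.0 = 2 and 2.5/0.5 = 5. Section 10.a describes ketones as acutely sensitive, and section 9.b lists them as a secondary outcome. Against this, the captions of Figures 1 and 2 report TNF-α and nitrotyrosine as lower at 8 weeks on either type of day in an alternate-day study. For the primary ratio the documents give no acute-day effect, so none can be calculated.

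**5. Split visit.** Assume the weekly cycle continues between the two parts, and take gaps of 1 to 7 days.

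- First part on C1: the second part falls on C2, N1, N2, N3, N4, N5, C1.
- First part on C2: it falls on N1, N2, N3, N4, N5, C1, C2.

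Either way, 5 of 7 possible gaps put the second part on a non-restricted day (5 of 6 if a gap of exactly 7 days is excluded). This counts possibilities and is not a probability.

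**6. Scope.** Section 10.b plans 20 completers per group, so the ambiguous rule covers all 20 in the 5-2 CR arm. That is the number exposed to the ambiguity, not the number shown to be affected.

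**The case against.** The contradiction itself cannot be disputed, so the case on the other side is about its weight.

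- **Ketones at week 8.** β-hydroxybutyrate is measured at the Outcome Visit and gives some objective indication of acute dietary state. This softens the point, but a low value cannot separate a different diet day from non-compliance, so it does not replace a recorded diet day.
- **Earlier samples.** Table 2 lists exosome plasma at weeks 2, 4 and 6, when the diet day is fixed. However, section 4.d.4 keeps that plasma for future studies, and the planned primary model does not use it.
- **Section 4.a.** Moving restriction to another day may be meant to keep a rescheduled visit on a restriction day. That is a fair reading, but the clause is permissive, does not address split visits and does not say which of the two days is wanted.
- **Split visits.** The visit-level sentences might be read as anchoring at least one part to a restriction day, but they disagree on which. The 5-of-7 count depends on the cycle continuing. The visit marks the end of the 8-week phase and Table 1 dispenses no shakes at week 8, so this may not happen. The gap in wording stands without the count.
- **Size.** The 1520 kcal and 1-versus-6-day figures describe the schedule and do not measure bias. The trial is an exploratory pilot at one clinical unit, the effect on the primary ratio could be nil, and a mixture of days is possible but not shown. All of this is true. The severity therefore rests on a contradictory rule for collecting the primary endpoint, which cannot be repaired once samples are taken.

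**Conclusion.** The concern holds and must be fixed: the text is wrong as written. Followed literally, it can put week-8 samples in the 5-2 CR arm in different acute dietary states, at the only post-baseline point of the planned primary contrast.

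The 1520 kcal gap rests on the plan's 2000 kcal/day assumption, and the 1-day versus 6-day lag on restriction days not being moved. No bias in the primary ratio is estimated or asserted. Confidence in the contradiction is high because the two sentences are explicit and nothing in the document reconciles them.

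**What to change.** Reconcile sections 4.d.1 and 4.d.5 so that both name the same single restriction day for every 5-2 CR participant. Which day is for the investigators to decide. In section 4.d.5, state how the rule applies to a split visit, with the primary blood sample on the named day, and how it applies when a restriction day has been moved under section 4.a. Record the diet day for each Outcome sample and procedure.

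The cost is wording in two sections, one extra data item and slightly less scheduling freedom. Sample size and analysis model stay as they are.

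A separate minor correction, which adds nothing to the severity here: section 4.d.1 lists randomisation before the Baseline Visit and section 4.d.3 places it at the end of that visit. The two should be aligned in the same edit.
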